7.1.1.4 Medical History

A medical history will be obtained by the investigator or qualified designee. The medical history will include all active conditions and any conditions diagnosed within the prior 10 years that are considered clinically significant by the Investigator. Details pertaining to the subject's prostate cancer diagnosis will be recorded separately and not listed as medical history.

7.1.1.4.1 History of Prostate Cancer

The investigator or qualified designee will obtain information regarding the subject's prostate cancer. This information will include but is not limited to the presentation at primary diagnosis, date and stage at primary diagnosis, date of and stage at most recent recurrence, and location of metastases at screening (if applicable).

7.1.1.5 Prior and Concomitant Medications Review

7.1.1.5.1 Prior Medications

The investigator or qualified designee will review and record prior medication taken by the subject within 28 days prior to the first dose of trial treatment.

7.1.1.5.2 Prior Treatment for Prostate Cancer

The investigator or qualified designee will review and report all prior treatments to prostate cancer including systemic treatments, radiation, and surgeries.

7.1.1.5.3 Concomitant Medications

The investigator or qualified designee will record medications taken by the subject during the trial up to 30 days after the last dose of trial treatment. All medications related to reportable SAEs and ECIs should be recorded as defined in Section 7.2.

7.1.1.5.4 Subsequent Anti-Cancer Therapy Status

The investigator or qualified designee will review all new anti-cancer therapy initiated after the last dose of trial treatment. If a subject initiates a new anti-cancer therapy within 30 days after the last dose of trial treatment, the 30-day Safety Follow-up visit must occur before the start of the new therapy. Once new anti-cancer therapy has been initiated, the subject will move into survival follow-up.

7.1.1.6 Assignment of Screening Number

All consented subjects will be given a unique screening number that will be used to identify the subject for all procedures that occur prior to randomization or treatment allocation. Each subject will be assigned only one screening number. Screening numbers must not be re-used for different subjects.

Any subject who is screened multiple times will retain the original screening number assigned at the initial screening visit.

Specific details on the screening visit requirements (screening/rescreening) are provided in Section 7.1.5.1.

7.1.1.7 Assignment of Treatment/Randomization Number

All eligible subjects will be allocated by non-random assignment and will receive a treatment/randomization number. The treatment/randomization number identifies the subject for all procedures occurring after treatment allocation/randomization. Once a treatment/randomization number is assigned to a subject, it can never be re-assigned to another subject.

Upon study completion, participants are discontinued from the current study and may be transitioned into a pembrolizumab extension study, if available. All participants in the extension study will be allocated by non-random assignment and will receive a treatment/randomization number. The treatment/randomization number identifies the participant for all procedures occurring after treatment allocation. This number will be unique from the treatment/ randomization number in the parent study.

7.1.1.8 Trial Compliance (Medication)

Interruptions from the protocol specified treatment plan for greater than 12 weeks between pembrolizumab (MK-3475) doses require consultation between the investigator and the Sponsor and written documentation of the collaborative decision on subject management.

Administration of trial medication will be witnessed by the investigator and/or trial staff. The total volume of trial treatment infused will be compared to the total volume prepared to determine compliance with each dose administered.

The instructions for preparing and administering pembrolizumab (MK-3475) will be provided in the Pharmacy Manual.

7.1.2 Clinical Procedures/Assessments

7.1.2.1 Adverse Event Monitoring

The investigator or qualified designee will assess each subject to evaluate for potential new or worsening AEs as specified in the Trial Flow Chart and more frequently if clinically indicated. Adverse experiences will be graded and recorded throughout the study and during the follow-up period according to NCI CTCAE Version 4.0 (see Section 12.6). Toxicities will be characterized in terms regarding seriousness, causality, toxicity grading, and action taken with regard to trial treatment.

All AEs of unknown etiology associated with pembrolizumab exposure should be evaluated to determine if they are events with potential immunologic etiology. See Section 5.6.1 regarding the identification, evaluation, and management of AEs of a potential immunological etiology.

Please refer to Section 7.2 for detailed information regarding the assessment and recording of AEs.

7.1.2.2 Physical Exam

7.1.2.2.1 Full Physical Exam

The investigator or qualified designee will perform a complete physical exam during the screening period and at treatment discontinuation. Clinically significant abnormal findings at screening should be recorded as medical history. New clinically significant abnormal findings at treatment discontinuation should be recorded as AEs.

7.1.2.2.2 Directed Physical Exam

The investigator or qualified designee will perform a directed physical exam, as clinically indicated, prior to dosing on Day 1 of each treatment cycle. New clinically significant abnormal findings should be recorded as AEs.

7.1.2.3 Vital Signs

The investigator or qualified designee will assess vital signs at screening, prior to dosing on Day 1 of each treatment cycle and at treatment discontinuation. Vital signs include temperature, heart rate, respiratory rate, weight and blood pressure. Height will be measured at screening only.

7.1.2.4 12-Lead ECG

A standard 12-lead ECG will be performed once at the screening visit using local standard procedures. Clinically significant abnormal findings should be recorded as medical history.

7.1.2.5 Eastern Cooperative Oncology Group (ECOG) Performance Scale

The investigator or qualified designee will assess ECOG Performance Status (see Section 12.5) at screening and prior to dosing on Day 1 of each treatment cycle through Cycle 8. After Cycle 8, ECOG Performance Status will be assessed at every other cycle (Cycles 10, 12, 14) and at treatment discontinuation.

7.1.2.6 Tumor Imaging and Assessment of Disease

The process for image collection and transmission to the central imaging vendor can be found in the Site Imaging Manual (SIM).

Tumor imaging should be acquired by CT (strongly preferred) and radionuclide bone scan. Magnetic resonance imaging should be used where CT is contraindicated or for imaging in the brain. The same imaging technique regarding modality and use of contrast should be used in a subject throughout the trial to optimize the visualization of existing and new tumor burden. Tumor imaging by both CT (or MRI) and radionuclide bone scan is required at every scheduled imaging time point.

All scheduled images for all subjects must be submitted to the central imaging vendor. Imaging obtained at unscheduled time points must also be sent to the central imaging vendor if the images support new or worsening metastatic disease based on site assessment.

Central review of baseline scans will be used to determine cohort assignment. Local review of imaging will be used for subject management. The central imaging vendor will receive radiologic images during the course of the study and will perform an analysis of response to treatment.

7.1.2.6.1 Initial Tumor Imaging

Initial tumor imaging at screening must be performed within 28 days prior to the date of first dose of trial treatment. Tumor imaging by both CT (or MRI) and radionuclide bone scan is required at screening.

Scans performed as part of routine clinical management are acceptable for use as the screening scans if they are of diagnostic quality, performed within 28 days prior to the date of first dose of trial treatment and can be assessed by the central imaging vendor.

Confirmation of measurable disease per RECIST 1.1 by central imaging vendor will be used to determine cohort assignment. Subjects with measurable disease per RECIST 1.1 will be enrolled in Cohorts 1, 2, and 4. Subjects with detectable bone metastases by whole body bone scintigraphy and no RECIST 1.1-measurable tumors will be enrolled in Cohorts 3 and 5.

The Sponsor allows for evaluation and follow-up of up to 10 soft tissue lesions (RECIST 1.1).

At screening, all lesions seen by CT (or MRI) and radionuclide bone scan will be documented. In determining response to treatment or progression, investigators must evaluate all target and non-target lesions and search for new lesions at each imaging time point.

7.1.2.6.2 Tumor Imaging During Trial

In the first year, on study imaging assessments must be performed every 9 weeks (63 days \pm 7 days) from the date of allocation for the first year (through week 54 \pm 7 days). Subjects who remain on treatment beyond the first year will have imaging performed every 12 weeks (84 days \pm 7 days). Imaging timing should follow calendar days from date of allocation and should not be adjusted for delays in cycle starts.

Response

Per RECIST 1.1, response should be confirmed by a repeat radiographic assessment not less than 4 weeks from the date response was first documented. The scan for confirmation of response may be performed \geq 4 weeks after the first indication of response or at the next scheduled scan, whichever is clinically indicated. Subjects who obtain a repeat scan do not need to undergo the next scheduled imaging if it is $<$ 4 weeks after the confirmation scan. Subjects will return to their regular imaging schedule starting with the next time point.

For any subject with known brain metastases at baseline, and who achieves a CR during trial treatment, a follow-up brain scan is required for confirmatory assessment of CR.

Progression

Radiographic progression for soft tissue lesions will be determined according to RECIST 1.1 (Section 12.7). Disease progression in soft tissue lesions should be confirmed by the site \geq 4 weeks after the first radiologic evidence of PD. Subjects who have unconfirmed disease progression and are clinically stable may continue on treatment at the discretion of the investigator until progression is confirmed by the site. Subjects who obtain a repeat scan do not need to undergo the next scheduled imaging if it is $<$ 4 weeks after the confirmation scan. Subjects will return to their regular imaging schedule starting with the next time point.

Subjects who have confirmed disease progression, as assessed by the site, will discontinue treatment.

Radiographic progression for bone lesions will be determined as described in the consensus guidelines of the Prostate Cancer Clinical Trials Working Group 3 (PCWG3) [44]. Radiographic progression of bone lesions will be defined as the appearance of ≥ 2 new bone lesions on radionuclide bone scan. Progression in bone at the first scheduled assessment at Week 9, if unaccompanied by soft tissue progression, requires a second radionuclide bone scan ≥ 6 weeks later. Progression is confirmed to have occurred at the first scheduled assessment if the confirmation bone scan shows ≥ 2 additional new lesions. Radiographic bone progression after the 9 week assessment must be confirmed ≥ 6 weeks later, if unaccompanied by soft tissue progression. Progression is confirmed if the confirmation bone scan shows the persistence of ≥ 2 new bone lesions. Subjects who have unconfirmed disease progression and are clinically stable may continue on treatment at the discretion of the investigator until progression is confirmed by the site. Subjects who have confirmed disease progression, as assessed by the site, will discontinue treatment.

If a subject with confirmed radiographic progression is clinically stable or clinically improved, and there is no further increase in the tumor dimensions at the confirmatory scan, an exception may be considered to continue treatment upon consultation with the Sponsor. Clinically stable subjects should also have at the confirmatory scan no further increase in the target lesions, no unequivocal increase in non-target lesions and no additional new lesions develop (non-worsening PD) to continue study treatment.

Imaging should continue to be performed until documented disease progression, the start of new anti-cancer treatment, withdrawal of consent or death, whichever occurs first (Table 5).

Table 5 Imaging and Treatment after 1st Radiologic Evidence of PD

	Clinically Stable		Clinically Unstable	
	Imaging	Treatment	Imaging	Treatment
1 st radiologic evidence of PD	Repeat imaging at ≥ 4 weeks to confirm PD (soft-tissue progression) Repeat bone scan at ≥ 6 weeks to confirm PD (bone progression)	May continue study treatment at the Investigator's discretion while awaiting confirmatory scan	Repeat imaging at ≥ 4 weeks to confirm PD if possible (soft-tissue progression) Repeat bone scan at ≥ 6 weeks to confirm PD if possible (bone progression)	Discontinue treatment
Repeat scan confirms PD	No additional imaging required	Discontinue treatment (exception noted in Section 7.1.2.6)	No additional imaging required	N/A
Repeat scan shows SD, PR or CR	Continue regularly scheduled imaging assessments every 9 weeks (every 12 weeks after 12 months)	Continue study treatment at the Investigator's discretion	Continue regularly scheduled imaging assessments every 9 weeks (every 12 weeks after 12 months)	May restart study treatment if condition has improved and/or clinically stable per Investigator's discretion

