7.1.2.6.4 Second Course (Retreatment) Tumor Imaging

A scan must be performed within 28 days prior to restarting treatment with pembrolizumab. Local reading (investigator assessment with site radiology reading) will be used to determine eligibility. Imaging should be submitted to the central imaging vendor for retrospective review.

On study imaging assessments should be performed every 9 weeks (63 days \pm 7 days) after the restart of treatment or more frequently if clinically indicated.

If tumor imaging shows initial PD (Section 7.1.2.6.), tumor assessment should be repeated \geq 4 weeks later in order to confirm PD with the option of continuing treatment while awaiting radiologic confirmation of progression. Subjects who obtain a confirmation scan do not need to undergo scheduled tumor imaging if it is $<$ 4 weeks later and may wait until the next scheduled imaging time point if clinically stable.

Per PCWG3, if radionuclide bone scan shows progression in bone, a radionuclide bone scan should be repeated \geq 6 weeks later in order to confirm PD with the option of continuing treatment while awaiting radiologic confirmation of progression. Subjects who obtain a confirmation bone scan do not need to undergo the next scheduled bone scan and may wait until the next scheduled time point if clinically stable.

Imaging should continue to be performed until disease progression, the start of new anti-cancer treatment, withdrawal of consent, death, or notification by the Sponsor, whichever occurs first.

In subjects who discontinue trial treatment, tumor imaging should be performed at the time of treatment discontinuation (\pm 4 week window). If a previous scan was obtained within 4 weeks prior to the date of discontinuation, then a scan at treatment discontinuation isn't mandatory.

In subjects who discontinue trial treatment due to documented disease progression, this is the final required tumor imaging. In subjects who discontinue trial treatment without documented disease progression, every effort should be made to continue monitoring their disease status by radiologic imaging using the same schedule the subject was on during treatment (e.g. every 9 weeks from the date of allocation or every 12 weeks [63 days \pm 7 days] from the date of allocation) until: 1) the start of new anti-cancer treatment, 2) disease progression, 3) death or 4) the end of the study, whichever occurs first.

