### 3.6 Statistical Methods

#### 3.6.1 Statistical Methods for Efficacy Analyses

For ORR, DCR and PSA response rate, the point estimate and 95% confidence interval will be provided using the exact binomial method proposed by Clopper and Pearson (1934) [3]. Subjects in the analysis population without response data will be counted as non-responders.

For rPFS, DOR, time to PSA progression, duration of PSA response, time to initiation of cytotoxic chemotherapy, time to new-anticancer therapy, time to first skeletal-related event, and OS, Kaplan-Meier (KM) curves and median estimates from the KM curves will be provided as appropriate.

Censoring rules for DOR are summarized in [Table 1](#).

Table 1 Censoring Rules for DOR

Situation	Date of Progression or Censoring	Outcome
No progression nor death, no new anti-cancer therapy initiated	Last adequate disease assessment	Censor (non-event)
No progression nor death, new anti-cancer therapy initiated	Last adequate disease assessment before new anti-cancer therapy initiated	Censor (non-event)
Death or progression immediately after $\geq 2$ consecutive missed disease assessments or after new anti-cancer therapy, if any	Earlier date of last adequate disease assessment prior to $\geq 2$ missed adequate disease assessments and new anti-cancer therapy, if any	Censor (non-event)
Death or progression after $\leq 1$ missed disease assessments and before new anti-cancer therapy, if any	PD or death	End of response (Event)
A missed disease assessment includes any assessment that is not obtained or is considered inadequate for evaluation of response.		

Censoring rules for rPFS are summarized in [Table 2](#).

Table 2 Censoring Rules for Analyses of rPFS

Situation	Rule
PD or death documented after $\leq 1$ missed disease assessment, and before new anti-cancer therapy, if any	Progressed at date of documented PD or death
PD or death documented immediately after $\geq 2$ consecutive missed disease assessments or after new anti-cancer therapy, if any	Censored at last disease assessment prior to the earlier date of $\geq 2$ consecutive missed disease assessment and new anti-cancer therapy, if any
No PD and no death; and new anticancer treatment is not initiated	Censored at last disease assessment
No PD and no death; new anticancer treatment is initiated	Censored at last disease assessment before new anticancer treatment

[Table 3](#) summarizes the key efficacy analyses.

Table 3 Analysis Strategy for Key Efficacy Variables

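### A CT-only confirmation scan less than 4 weeks before the next scheduled visit can also waive that visit's bone scan, leaving 18 to 24 weeks between bone scans

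*Protocol*

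**What the plan says.** - **Schedule (Protocol 7.1.2.6.2).** In the first year, "on study imaging assessments must be performed every 9 weeks", counted from allocation. Later, "Subjects who remain on treatment beyond the first year will have imaging performed every 12 weeks".
- **Content of a scheduled visit (Protocol 7.1.2.6).** "Tumor imaging by both CT (or MRI) and radionuclide bone scan is required at every scheduled imaging time point". The rule is worded for scheduled time points.
- **Confirmation (Protocol 7.1.2.6.2 and Table 5).** A response is confirmed by repeat radiography at least 4 weeks later, or at the next scheduled scan. Table 5 lists repeat imaging for soft-tissue progression (at least 4 weeks) separately from a repeat bone scan for bone progression (at least 6 weeks).
- **Waiver (Protocol 7.1.2.6.2, under Response and under Progression).** "Subjects who obtain a repeat scan do not need to undergo the next scheduled imaging if it is" less than 4 weeks after the confirmation scan. Then: "Subjects will return to their regular imaging schedule starting with the next time point". No modality is named.
- **Second course (Protocol 7.1.2.6.4).** There is a similar soft-tissue waiver, also without a modality, and a separate bone sentence: "Subjects who obtain a confirmation bone scan do not need to undergo the next scheduled bone scan".
- **Censoring (sSAP 3.6.1).** For DOR and rPFS, progression after at most one missed assessment is an event; progression immediately after two or more consecutive missed assessments is censored. The Table 1 footnote adds: "A missed disease assessment includes any assessment that is not obtained or is considered inadequate for evaluation of response".
- **Endpoints (sSAP 3.4.1).** PCWG3-modified DOR and rPFS both use the bone scan to determine progression.

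**The concern.** Skipping a scan is reasonable for a modality imaged less than 4 weeks earlier. It is not reasonable for a modality that was not repeated. If only the CT is repeated to confirm a response, the last bone scan is still the one from the index visit, and the waiver can remove the next one.

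Bone progression arising in that interval is then first seen one full imaging interval later. The error runs in one direction and lengthens time to progression. It falls mainly on responders, who make up the whole DOR population. It also treats the two DOR endpoints unequally, because CT spacing stays much closer to schedule than bone-scan spacing. Responders may be few: the 10% rows of the sample-size table give 20 of 200 and 8 of 80.

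**Working it through.** **1. The plan's intervals.** 9 × 7 = 63 days and 12 × 7 = 84 days, as stated. Six visits fall in year 1 (54 / 9 = 6). The calendar is weeks 9, 18, 27, 36, 45, 54, 66, 78, 90 and so on. The documents give no figure for the bone-scan gap after a waiver.

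**2. When the waiver applies.** Let L be the days from the index scan to the next scheduled visit, and c the days from the index scan to the confirmation scan. Confirmation needs c ≥ 28. The waiver needs L − c < 28.
- Year 1, L = 63: c > 35, so days 36 to 62. That is 27 of the 35 possible unscheduled days (28 to 62).
- Year 2, L = 84: c > 56, so days 57 to 83. That is 27 of 56 days (28 to 83).
- At the 4-week minimum, 63 − 28 = 35 days (5 weeks) or 84 − 28 = 56 days (8 weeks) remain, so nominally nothing is waived.
- With the ±7-day windows, an index scan at day 63 + 7 confirmed 28 days later falls on day 98. A next visit at day 126 − 7 = 119 is 21 days away, so the waiver can apply in year 1. In year 2 the same steps give 455 − 413 = 42 days, so it cannot.
- Confirming at the next scheduled visit waives nothing, and that visit includes a bone scan.

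These are counts of calendar days, not probabilities.

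**3. Bone-scan gap if the confirmation was CT-only and the waiver was used.**

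| Index visit | Skipped visit | Next bone scan | Gap (weeks) | With ±7-day windows | Late dating (weeks) |
|---|---|---|---|---|---|
| Week 9 | Week 18 | Week 27 | 18 | 16–20 | 9 |
| Week 45 | Week 54 | Week 66 | 21 | 19–23 | 12 |
| Week 54 | Week 66 | Week 78 | 24 | 22–26 | 12 |

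Late dating is the time from the skipped visit to the next bone scan. It applies to bone progression that the skipped scan would have shown. If onset is uniform over the gap, the mean detection lag rises from 4.5 to 9 weeks (18-week gap) or from 6 to 12 weeks (24-week gap).

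**4. CT spacing for comparison.** In the 18-week case the gap from confirmation CT to next CT is 126 − c. That runs from 126 − 62 = 64 days (9.1 weeks) to 126 − 36 = 90 days (12.9 weeks).

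**5. Conditional size.** The documents give no time to bone progression, so I assume an exponential time with median m of 4 to 12 months. The chance of onset in a skipped interval of w weeks is 1 − 2^(−w/m), with m in weeks.

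| Median | w = 9 | Mean inflation (× 9 weeks) | w = 12 | Mean inflation (× 12 weeks) |
|---|---|---|---|---|
| 4 months | 30% | 2.7 weeks | 38% | 4.6 weeks |
| 6 months | 21% | 1.9 weeks | 27% | 3.3 weeks |
| 9 months | 15% | 1.3 weeks | 19% | 2.3 weeks |
| 12 months | 11% | 1.0 weeks | 15% | 1.8 weeks |

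These figures apply per subject who had a CT-only confirmation in the trigger window and used the waiver. They ignore soft-tissue progression or death coming first.

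**6. Censoring.** One waived visit is at most one missed assessment, so progression remains an event, at the late date. Censoring would need a further, consecutive missed visit.

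**The case against.** The strongest case on the other side is that the gap needs several things at once. The waiver is optional and conditional on timing. A CT-only confirmation is an inference: 7.1.2.6 describes tumor imaging as CT plus bone scan, and the flow chart row for tumor imaging lists both. The Site Imaging Manual, which is not among the documents, may require both modalities at confirmation. All of this stands as a limit on how often the gap occurs. It does not remove the gap, because the protocol's both-modalities rule covers scheduled time points only and Table 5 separates the two kinds of repeat.

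Some stronger readings are tempting but not supported:
- **Every confirmation scan cancels the next visit.** It does not; see the timing in step 2.
- **The waiver contradicts 7.1.2.6.** A specific, conditional waiver is an exception to a general rule. The two passages, and the Table 5 instruction to continue regular imaging when progression is not confirmed, simply do not refer to each other.
- **The second-course section already has this right.** Only its bone sentence is modality-specific. Its soft-tissue waiver leaves the same opening.
- **rPFS is inflated for everyone treated through a first soft-tissue progression.** If central review agrees with that first progression, the event is already dated there, and confirmed progression needs no further imaging.
- **A waiver turns progressions into censored observations.** One waiver alone cannot do this.

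**Conclusion.** As written, the waiver lets a CT-only confirmation remove a scheduled bone scan. Where that happens, bone scans are 18, 21 or 24 weeks apart, and bone progression that the skipped scan would have shown is dated 9 or 12 weeks late.

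The bias is upward and falls mainly on PCWG3-modified DOR in responders. rPFS is affected only for responders and for subjects whose first soft-tissue progression is not called by central review. ORR is not shown to be affected.

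The gaps follow from the protocol calendar. Two things remain open. How many subjects have a CT-only confirmation in the trigger window and use the waiver is unknown, so no shift in any cohort's median is shown. The 11–30% and 1.0–2.7 weeks (year 1) rest on the assumed 4–12 month median. The conclusion also assumes that the Site Imaging Manual does not require a bone scan at confirmation. The point is worth fixing because the delay runs in one direction and the correction is small.

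**What to change.** - **Protocol 7.1.2.6.2, both waiver sentences, and the soft-tissue waiver sentence in 7.1.2.6.4.** Limit the waiver to the modality repeated at confirmation, for example: a modality repeated at confirmation need not be repeated at the next scheduled time point if that falls less than 4 weeks later; the other modality is performed as scheduled. With this wording a CT-only confirmation leaves the bone-scan interval at 9 weeks (12 after year 1), and the added delay is zero.
- **sSAP Tables 1 and 2.** State that an assessment waived under these sections is not a missed assessment. This is a minor clarification, because a single missed visit does not cause censoring. It is useful even if most imaging is complete.

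The cost is three protocol sentences and one footnote in each of two sSAP tables. No scan is added to the planned calendar. The downside is that some subjects will have a scheduled bone scan they could otherwise have skipped.
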